3 INVESTIGATIONAL PRODUCT

3.1 TEST ARTICLE

3.1.1 HPV Peptides

PepCan will contain four HPV 16 E6 peptides: E6 1-45 (Ac-MHQKRTAMFQDPQERPRKLPQLCT ELQTTIHDIIILECVYCKQQLL-NH2), E6 46-80 (Ac-RREVYDFAFRDLCIVYRDGNPYAVCDKC LKFYSKI-NH2), E6 81-115 (Ac-SEYRHYCYSLYGTTLEQQYNKPLCDLLIRCINCQK-NH2), and E6 116-158 (Ac-PLCPEEKQRHLDKKQRFHNIRGRWTGRCMSCCRSSLRRETQL-NH2) (US Patent No. 8,652,482). Commercially produced cGMP-grade peptides (CPC Scientific, San Jose, CA) will be examined.

The four peptides will be provided in a single vial in lyophilized form at the 50 µg/peptide/dose, and will be stored at -80°C (±10°C) except during shipping and immediately prior to use.

The UAMS Research Pharmacy will be responsible for peptide receipt, storage, and preparation prior to vaccination visits.

3.1.2 Candin®

Candida Albicans Skin Test Antigen for Cellular Hypersensitivity will be supplied in the commercially marketed drug Candin®. The vials will be stored at 2°C to 8°C as directed by the package insert until use. This product is approved for multi-dosing. The dose of Candin® per injections for this study is 0.3 mL.

3.1.3 Combining HPV Peptides and Candin®

Sterile water will be added to a vial containing the four cGMP peptides on the day of use. Reconstituted peptides will be drawn in a syringe depending on the dose level, and 0.3 mL of Candin® will be drawn into the same syringe. The combined peptide-Candin® mixture should be kept on ice or in refrigerator until immediately before injection.

3.1.4 Temperature Logs

Daily temperature logs will be maintained by the Pharmacy per standard operating procedures of the Pharmacy. Any deviations in temperature range will be reported to the Sponsor and Principal Investigator.

3.1.5 Drug Accountability Records

Drug accountability records will be maintained per Pharmacy, Institutional, FDA, NIH, and other applicable policies.

3.2 TREATMENT REGIMEN

Subjects will receive four injections of PepCan (50 µg/peptide/injection) via intradermal injection in the extremities with three weeks between each injection.

4 STUDY DESIGN

[figure not shown]
4.1 OVERVIEW

This is a single site Phase II clinical trial of PepCan for treating women with biopsy-proven HSILs randomized and double-blinded to two treatment arms. Half of the subjects will receive PepCan, and the other half will receive Candin® alone. The study design closely resembles the latest guidelines for treating young women with HSIL [14]. Study subjects will be patients attending the UAMS Obstetrics and Gynecology Clinics with untreated biopsy-proven HSILs and patients referred from other clinics. Four injections (one every 3 weeks) of PepCan or Candin® will be intradermally administered in the extremities. Clinical response will be assessed by comparison of colposcopy-guided biopsy results obtained prior to vaccination and at 12-Month Visit. Safety will be monitored from the time of enrollment through the 12-Month Visit. Blood will be drawn for laboratory testing and immunological analyses (“blood test”) prior to injection, after the second vaccination, 6 months after the fourth vaccination, and 12 months after the fourth vaccination. Blood will be drawn to aid T-cell analyses (“blood draw”) after the first and third vaccinations, and possibly at the Optional Follow-Up and/or Optional LEEP visits. HPV-DNA testing will be performed at Screening and 6- and 12-Month Visits (Fig. 6). If a subject has persistent HSIL at the 12-Month Visit or if a subject is withdrawn due to excessive toxicity, she will be given an option to return for a LEEP visit. Alternatively, she may choose to exit the study and be followed by a gynecologist for up to 2 years of observation as recommended before surgical treatment [14].

4.2 RANDOMIZATION TO TREATMENTS

The study randomization schematic will be constructed by the study Statistician. Randomization will occur after Subject eligibility for vaccinations has been confirmed. Subjects will be randomized in a 1:1 ratio to PepCan or Candin® alone. Randomization will be done in book form by Research Pharmacy.

Fig. 6 Schematic presentation of study visits scheduled for the Phase II clinical trial of our HPV therapeutic vaccine. Colpo, colposcopy, Bx, biopsy, ECC, endocervical curettage, LEEP, loop electrosurgical excision procedure. [†]These blood tests are for clinical analyses only. ^{*}These blood tests are for scientific analyses only. Blood tests may be drawn as needed for clinical and/or scientific analyses during any optional visit.

4.3 MONITORING TOXICITY

Serious toxicity will be defined (using CTCAE v 4.03) as drug-related:

- Grade II or higher allergic reactions. Grade II is defined as “intervention or infusion interruption indicated; responds promptly to symptomatic treatment (e.g., antihistamines, NSAIDS, narcotics); prophylactic medications indicated for ≤ 24 hours”. Grade III is defined as “prolonged (e.g., not rapidly responsive to symptomatic medication and/or brief interruption of infusion); recurrence of symptoms following initial improvement; hospitalization indicated for clinical sequelae (e.g., renal impairment, pulmonary infiltrates)”.
- Grade II or higher autoimmune reactions. Grade II is defined as “evidence of autoimmune reaction involving a non-essential organ or function (e.g., hypothyroidism)”. Grade III is defined as “autoimmune reactions involving major organ (e.g., colitis, anemia, myocarditis, kidney)”.
- Any Grade III or higher event.

Any subject who experiences serious toxicity will be discontinued from the study.

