2.2 SECONDARY OBJECTIVE: SAFETY

Safety will be assessed by documenting AEs from the time of enrollment until the 12-Month Visit according to CTCAE v4.03.

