6.2 STUDY VISIT WINDOWS

6.2.1 Between Visits of an Individual Subject

- The first vaccination visit (Visit 1) should be scheduled as soon as possible after all results from the screening visit are available, and subjects are deemed qualified to continue to the vaccination phase of the study, but no later than 60 days after the day punch biopsy was obtained (the screening day for most of the subjects).
- The subsequent vaccination visits (Visits 2-4) should be scheduled 3 weeks \pm 7 days apart.
- The 6-Month Visit should be scheduled 6 months \pm 2 weeks following Visit 4
- The 12-Month Visit should be scheduled 6 months \pm 2 weeks following 6-Month Visit.
- Optional LEEP visit (if subject chooses) should be scheduled as soon as possible after 12-Month Visit or after determining a subject needs to be withdrawn due to serious toxicity.

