6.12 IF THE SUBJECT DID NOT COMPLETE THE STUDY

Subjects may not complete the study for a variety of reasons including serious toxicity, non-compliance, lost to follow-up, etc. In these instances, and for subjects who completed at least one vaccination visit, the study coordinator will ensure that subjects complete the “Early Termination Questionnaire” over the phone, via e-mail, or by mail (no stamp will be provided).

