7.1.2 Subjects Who Do Not Complete the Study

- If a subject is withdrawn due to vaccine-related toxicity (see stopping rules), due to becoming pregnant because contraception failure, or in cases of advancing disease after at least one completed vaccination visit, a check in the amount of \$300 will be mailed to an address provided by the subject once the “Early Termination Questionnaire” has been completed.
- For subjects who terminated early but not because of toxicity or due to non-compliance including cases of consequent pregnancies, \$50 per visit for each of Visits 1-4, the 6-Month Visit, and 12-Month Visit completed will be mailed if the subject completes the “Early Termination Questionnaire”. No compensation will be provided for the Screening Visit, Optional Follow-Up Visit(s), and Optional LEEP Visit.

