9.4 FACTORS CONTRIBUTING TO STUDY RECRUITMENT AND RETENTION

Based on data provided in "Screening Visit Questionnaire", "Early Termination Questionnaire", and "12-Month Visit Questionnaire", factors that contribute to subject recruitment and retention may be assessed. The Fisher's exact test will be used to compare factors such as frequent use of Facebook private group, motivation for entering the study, or having young children will be compared between the subjects who are withdrawn from the study early and the subjects who completed the study.

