10.2 ADVERSE EVENTS MONITORING

10.2.1 Time Period

Adverse events will be collected from the time of enrollment until the 12-Month Visit.

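### Section 4.3 takes women with drug-related serious toxicity off the study, not only off injections, which ends their required 6- and 12-Month Visits and 12-month biopsy

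*Protocol*

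**What the plan says.** Protocol 4.3 defines serious toxicity as drug-related Grade II or higher allergic or autoimmune reactions, or any drug-related event of Grade III or higher. The consequence is: "Any subject who experiences serious toxicity will be discontinued from the study".

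Other sections read the same way:

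- 4.1: "if a subject is withdrawn due to excessive toxicity, she will be given an option to return for a LEEP visit".
- 6.2.1 times that LEEP as soon as possible "after determining a subject needs to be withdrawn due to serious toxicity".
- 6.12: "Subjects may not complete the study for a variety of reasons including serious toxicity". Its one required step, after at least one vaccination visit, is the Early Termination Questionnaire.
- 7.1.2 sets her payment under the heading for women who do not complete.

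The AE window has no exception for these women. Section 10.2.1 says: "Adverse events will be collected from the time of enrollment until the 12-Month Visit". Sections 2.2 and 4.1 give the same end point. The SAP (III. Safety) instead closes the window at the last study visit.

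Section 9.1 keeps all women who qualified for vaccination in the intention-to-treat (ITT) analysis, and 9.2 keeps everyone with at least one dose in the safety assessment. The SAP's per-protocol set consists of women who completed the 12-month assessment.

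**The concern.** The women removed are those with the most important related events. The listed autoimmune examples include hypothyroidism, colitis, myocarditis and kidney involvement, where the later course matters. Yet their required observation is cut short. They stay in the safety set with shorter follow-up than other women. They also stay in the ITT set without the biopsy that defines the primary outcome, and they leave the 12-month completer set by rule. Because the loss follows from tolerance of the product, it cannot be taken as random.

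The rule is also wider than withholding a dose requires. It covers Grade II allergic reactions, which 4.3 itself describes as settling promptly with symptomatic treatment. After injection 4 no dose remains to withhold, so the only effect is to end required follow-up. For pregnancy, by contrast, 4.5.1 leaves removal to a medical monitor's judgement.

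**Working it through.** **1. What is left after removal.** Required: the questionnaire. Its content is not shown. It triggers payment (7.1.2) and treatment disclosure (1.6.4), and its only stated analytic use is in 9.4, where "factors that contribute to subject recruitment and retention may be assessed". Optional: LEEP and follow-up visits. Section 6.11.1 allows follow-up after early exit and for AE evaluation, 6.11.2 allows laboratory tests, and Appendix 1 marks AE recording at both kinds of visit. None has a fixed schedule or includes the 12-month quadrant biopsies. Section 10 contains no rule to follow an event to resolution.

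**2. Required follow-up lost.** Inputs from 6.2.1: injections 3 weeks apart, the 6-Month Visit 6 months after Visit 4, and the 12-Month Visit 6 months after that. Ignoring visit windows, removal right after injection k loses (4 − k) × 3 weeks + 12 months:

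- k = 1: 9 weeks (2.07 months) + 12 = 14.1 months
- k = 2: 6 weeks (1.38 months) + 12 = 13.4 months
- k = 3: 3 weeks (0.69 months) + 12 = 12.7 months
- k = 4: 12.0 months
- toxicity found at the 6-Month Visit: about 6 months

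**3. How many women.** The plan gives no expected rate. Phase I (1.4.1 to 1.4.3) vaccinated 4 × 6 + 10 = 34 women, of whom 6 + 10 = 16 had 50 µg, with no related dose-limiting toxicity (DLT). The DLT definition in 1.2 is close to the one in 4.3. For zero events the exact two-sided 95% upper limit is 1 − 0.025^(1/n):

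- n = 34: 1 − 0.025^(1/34) = 10.3%, or 0.103 × 40 ≈ 4 women per arm
- n = 16: 1 − 0.025^(1/16) = 20.6%, or 0.206 × 40 ≈ 8 women per arm

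These are upper limits, not expectations. All 34 women received PepCan, and the Phase I assessment LEEP came about 3 months after the last injection. There are no data here for Candin alone in this population.

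**4. Power.** Section 1.5.9 states 91% for 35 PepCan completers at 60% against 34 of 117. A two-sample normal calculation uses Φ{(d − 1.96·√[p̄(1 − p̄)(1/n₁ + 1/n₂)]) / √[p₁(1 − p₁)/n₁ + p₂(1 − p₂)/n₂]}. With d = 0.600 − 0.291 = 0.309 and p̄ = (21 + 34)/152 = 0.362, this is Φ{(0.309 − 0.181)/0.0928} = Φ(1.38) = 91.6%, which reproduces the plan.

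As a severe case, remove 8 of 40 and apply 5% attrition per year (5.2) over 16 months (5.3): 32 × (1 − 0.067) ≈ 30 completers. Power is then 88.3% by the same formula. With the exact one-sample binomial test named in 9.1 it is 95.2%, against 97.0% at 35. If the response rate among the remaining women stays at 60%, power is not the issue.

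**The case against.** The strongest case is that safety follow-up after exit already exists. Optional visits can be booked for AE evaluation, AEs are recorded there, and serious, unexpected, drug-related events have expedited reporting (10.3.2). The protocol's AE window can be read as a general statement, and the SAP's last-study-visit wording fits early exit. Section 4.1 even lists exiting the study as an alternative to LEEP, so withdrawal is not used with perfect consistency. This narrows the AE gap. It does not close it, because nothing requires a visit, and none of it restores the 6- and 12-Month Visits or the biopsy.

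Second, these women have biopsy-proven HSIL and have lost their study treatment. Section 1.5.9 regards leaving CIN2/3 untreated for 12 months in a placebo group as hard to justify, so prompt LEEP is defensible. After LEEP, a later biopsy no longer measures vaccine response. This stands and shapes the fix, but LEEP is optional, and a woman who declines it still has an informative 12-month biopsy.

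Third, the ITT denominator keeps these women, and the historical control is handled in that spirit (34 responders over 117, 138 or 149). Sections 2.1, 8.1 and 9.1 also allow a supplementary analysis with 6-month histology. These points limit the efficacy harm. But counting a woman in the denominator is not the same as observing her result, and neither document writes out how a missing 12-month biopsy is scored.

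Fourth, keeping the biopsy would bring partly dosed women into the completer set, and continued follow-up raises the question of when treatment is disclosed. Both are fair and need explicit wording.

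**Conclusion.** The point holds as a design weakness worth correcting. As written, 4.3 ends required follow-up and the 12-month biopsy for women with drug-related serious toxicity. The loss is about 12 to 14 months per woman when toxicity occurs at an injection, and about 6 months when it is found at the 6-Month Visit. The number of women is probably small. Phase I is compatible with rates up to 10.3% (all doses) or 20.6% (50 µg), assuming that its DLT definition stands in for 4.3 and that its shorter observation carries over.

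Four stronger readings are tempting but unsupported:

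- That AE capture stops altogether. Section 6.11 and Appendix 1 allow it at optional visits.
- That these women drop out of the ITT or safety sets. Sections 9.1 and 9.2 keep them.
- That Phase I already had a qualifying case, from the Grade 3 hypokalemia at 50 µg in Table 2. The marks for unrelated events are not reliable in the available text of that table, and 1.4.3 says that none of the related or possibly related events, hypokalemia among them, exceeded Grade 2.
- That the trial loses its power. The working shows only a small change.

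**What to change.** In 4.3, replace discontinuation from the study with discontinuation from further injections. Then:

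- Unless consent is withdrawn, follow the toxicity to resolution, continue AE collection to the 12-Month Visit, and keep the scheduled 6- and 12-Month Visits with the 12-month biopsy.
- Keep prompt LEEP as an option. If it is done before the 12-Month Visit, record its histology and date for supplementary use, and do not count a later biopsy as vaccine response.
- Include these women in the ITT analysis with their observed 12-month result. State that the completer (per-protocol) set is shown with and without women who had fewer than four injections.
- Align 4.1, 6.2.1, 6.12, 7.1.2 and 1.6.4. Allow treatment disclosure before the 12-Month Visit only if her care needs it, and record it.

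The SAP's AE window can stay, since with visits kept the last study visit is normally the 12-Month Visit. The SAP is dated 8/4/23. If follow-up has finished, what remains is to report how many women left under 4.3 in each arm and how long their AEs were observed.

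The cost is wording plus a few women attending visits already in the schedule. No extra completion payment arises, because toxicity withdrawals already receive $300, as completers do (7.1.1, 7.1.2). Travel stipends of $40 to $100 per visit apply beyond 50 miles. The downside is that some later AE reports may come from unblinded women.

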4.4 INTERRUPTION

In case of prolonged unavailability of vaccine peptides, such as due to failing stability testing and need to manufacture a new lot, all subjects being vaccinated will receive Candin® for the remaining injections. Subjects starting vaccination will be assigned to the Candin® group. After a new lot of peptides become available, randomization will resume with the following possible modifications: (1) the number of subjects to be recruited in the Candin® group will be decreased by the number

of subjects recruited into the Candin® group during the interruption, and (2) the number of subjects in the PepCan group will be increased by the number of subjects who started out receiving PepCan but received Candin® during the interruption. To protect study blinding, UAMS ORRA Quality Assurance will communicate directly with Research Pharmacy and the statistical team. No information regarding which vaccination (PepCan or Candin®) any subjects are receiving will be revealed to the rest of the study team including the Principal Investigator.

4.5 STOPPING RULES

4.5.1 For subject

- A subject should be withdrawn from the study at any point if pelvic examination and histological analysis show evidence of an invasive squamous cell cervical carcinoma or if there is a clinical suspicion of having developed it based on signs and symptoms such as unexplained, prolonged vaginal bleeding. This is to allow the subject to receive the proper work-up and treatment. The subject may proceed to the optional LEEP visit if determined to be beneficial by a study physician. Should a cervical cancer diagnosis be confirmed during the subject's study participation, the subject may receive a hysterectomy if it is determined to be medically necessary.
- If a subject becomes pregnant during her participation in the study, a medical monitor will determine whether or not she should be removed from the study. Medical records will be requested to determine the health of the mother and child.

4.5.2 For study

- The study enrollment and vaccine administration will be suspended if any subject experiences vaccine-related Grade IV or higher AE. These activities can re-start only after notifying the applicable regulatory authorities and with a permission to resume from the Medical Monitor.
- The sponsor may decide to stop the study at any point, for any reason.

4.6 EMERGENCY UNBLINDING

If a medical emergency necessitating the identity of the vaccine administered occurs, the PI will notify Research Pharmacy and the study Statistician. Research Pharmacy will give identity of vaccine to PI and Study Coordinator and note any incidence in the Randomization book.

5 SUBJECT ENROLLMENT AND STUDY DURATION

5.1 SUBJECT POPULATION, RECRUITMENT, AND INFORMED CONSENT PROCESS

- Women, aged 18 to 50 years, seen at the UAMS Obstetrics and Gynecology Clinics and ANGELS Telecolposcopy program with recent Pap smear results positive for HSIL or "Cannot rule out HSIL" will be recruited through Physician referral, brochures, flyers, UAMS website, letters, phone calls, and word of mouth by study team; interested potential subjects will contact the study coordinator to discuss study; coordinator will conduct initial inclusion/exclusion criteria assessment, schedule subject for screening visit, and send a copy of the informed consent document for the subject to review.
- Other women with recent abnormal Pap smear results positive for HSIL or "Cannot rule out HSIL" will be recruited through clinic referral, brochures, flyers (distributed on and off campus), UAMS website, and advertisements in newspaper, radio, Google ad, and/or social networking site; interested potential subjects will contact the study coordinator to discuss study; coordinator will conduct inclusion/exclusion criteria assessment, schedule subject for

screening visit, and send a copy of the informed consent document for the subject to review; coordinator will request that subject obtain copy of Pap smear result from their physician's office and bring with them to the screening visit.

- Women with recent diagnosis (the duration between the day of diagnosis and the day of 1st injection needs to be \leq 60 days) of HSIL on colposcopy guided punch biopsy will be recruited through clinic referral, brochures, flyers (distributed on and off campus), UAMS website, and advertisements in newspaper, radio, letters, phone calls, Google ad, and/or social networking site; interested potential subjects will contact the study coordinator to discuss study; coordinator will conduct inclusion/exclusion criteria assessment, schedule subject for screening visit, and send a copy of the informed consent document for the subject to review; coordinator will request that subject obtain copies of medical records of abnormal biopsy from their physician's office and bring it with them to the screening visit.

5.1.1 Inclusion Criteria

- Aged 18-50 years
- Had recent (\leq 60 days) Pap smear result consistent with HSIL or “cannot rule out HSIL” or HSIL on colposcopy guided biopsy
- Untreated for HSIL or “Cannot rule out HSIL”
- Able to provide informed consent
- Willingness and able to comply with the requirements of the protocol

5.1.2 Exclusion Criteria

- History of disease or treatment causing immunosuppression (e.g., cancer, HIV, organ transplant, autoimmune disease)
- Being pregnant or attempting to be pregnant within the period of study participation
- Breast feeding or planning to breast feed within the period of study participation
- Allergy to *Candida* antigen
- History of severe asthma requiring emergency room visit or hospitalization within the past 5 years
- History of invasive squamous cell carcinoma of the cervix
- History of having received PepCan
- If in the opinion of the Principal Investigator or other Investigators, it is not in the best interest of the patient to enter this study

5.1.3 Informed Consent Process

- Potential subjects will be provided the informed consent form before the screening visit and allowed as much time as needed to make decisions regarding study participation.
- The study coordinator/study team member authorized by PI to administer informed consent discussion will discuss the study in detail (including the age-specific standard of care guidelines as periodically released by the American Society of Colposcopy and Cervical Pathology) with the potential subject at any time before the screening visit or at a UAMS Gynecology clinic when she arrives for the screening visit (prior to any study-related procedures), and answer any questions the subject may have about the study; discussions will be conducted in English or in Spanish by Spanish speaking interpreters.
- Should an enrolled subject become pregnant during the study period she will be provided with an informed consent addendum to verify whether or not the subject would agree to the

collection, storage and use of data about the pregnancy, birth and health of the baby. If the subject agrees, they will be asked to fill out an authorization form for release of information to UAMS.

- As consent is an ongoing process, subjects will be asked if they still wish to participate in the study prior to study procedures conducted at each study visit.

